7.4.1.6 Monitoring of Subjects with Adverse Events

AEs are recorded and assessed continuously throughout the trial and are assessed for final outcome at the End of Trial visit. All SAEs ongoing at the End of Trial visit must be monitored and followed up by the Investigator until stabilization or until the outcome is known, unless the subject is documented as "lost to follow-up". Reasonable attempts to obtain this information must be made and documented. It is also the responsibility of the Investigator to ensure that any necessary additional therapeutic measures and follow-up procedures are performed.

Monitoring of Specific Adverse Events

Not applicable.

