Unless otherwise specified in respective sections, missing data will not be replaced.

The handling of missing covariate and stratification factor information is described below.

The handling of missing DMD end date is described in Section 12.

Incomplete or missing onset dates of relapses from “MS Relapse Report” will be imputed as follows:

- In cases where the onset date is completely or partially missing but the onset month and year, or the onset year are equal to the start of study medication then the onset date will be replaced by the start date of study medication.
- In all other cases the missing onset day or missing onset month will be replaced by 1.

In all subject data listings, imputed values will be presented. In all listings imputed information will be flagged.

Missing statistics, e.g. when they cannot be calculated, should be presented as “nd”. For example, if n=1, the measure of variability (e.g. SD) cannot be computed and should be presented as “nd”.

Where tables are presented over time, the total of missing and non-missing observations at each time-point should reflect the population still in the study at that time. This does not apply when imputations are made beyond study withdrawal.

Data Handling in case of major PDs

Electronic Patient Reported Outcomes (ePRO) assessments performed completely in non-native language will not be used for the statistical summaries or analyses as planned in this IAP and will be flagged accordingly in any listings.

Any other PD will not be considered in the planned statistical analyses.

Covariates and stratification factors

- Age

Age (years) at time of Informed Consent (loaded from iRT). Missing age will be replaced as follows if used as a covariate:

1. Age will be estimated from the year of birth (year of IC – year of birth), as recorded in the electronic Case Report Form (eCRF)
2. If year of birth is missing, age will be imputed by the mean age of the FAS.

- **Pooled centers**

Some centers will have few eligible subjects only. Therefore, the centers will be pooled together in geographical groups by country and the Scandinavian countries will be further pooled together to one Scandinavian pool.

Software(s)

All analyses will be performed using SAS® Software version 9.3 or higher.

10 Trial Participants

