15.2.3 Other Significant Adverse Event

TEAEs associated to COVID-19

The frequency of TEAEs associated to COVID-19 will be presented. The relevant events will be identified based on the SMQ COVID-19 (narrow scope) and will be presented by SOC and PT.

Fatigue

The prevalence of fatigue will be presented for each month of the Course 1 Treatment Period and separately for each month of the Course 2 Treatment Period. The prevalence at a given month is defined as:

(Number of patients with fatigue during the month/ Number of patients with fatigue during the month or still in the study at the end of the month) * 100,
where patients with fatigue during the month are all patients who had at least one reported TEAE with PT equal to 'Fatigue' that either started during the month or is still ongoing from the previous month.

If the end date of the AE is partially or completely missing and the AE is not reported as ongoing, the end date will be imputed as follows:

- Day missing but month and year available: last day of the month,
- Day and month missing: last day of the year but not later than end of Treatment Period 2,
- Completely missing: end of Treatment Period 2

The results will be presented in a tabular as well as graphical manner. Course 1 and 2 Treatment Periods as well as duration of a month is defined in Section 9.

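### The monthly fatigue prevalence keeps exiting subjects in the denominator only if they had fatigue, so it can only err upward: slightly with ordinary withdrawal, possibly a lot in the last month of Course 2

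*SAP*

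**What the plan says.** SAP 15.2.3 (Fatigue) plans a table and a graph, by month within each course's period: "The prevalence of fatigue will be presented for each month of the Course 1 Treatment Period and separately for each month of the Course 2". The numerator is subjects with at least one fatigue TEAE "that either started during the month or is still ongoing from the previous month". The denominator is "Number of patients with fatigue during the month or still in the study at the end of the month".

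Stop dates are imputed only in one situation: "If the end date of the AE is partially or completely missing and the AE is not reported as ongoing". If day and month are missing, the date becomes the "last day of the year but not later than end of Treatment Period 2"; a wholly missing date becomes the end of that period. Nothing is said about an AE that is reported as ongoing. For periods and month length the section points elsewhere: "Course 1 and 2 Treatment Periods as well as duration of a month is defined in Section 9".

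SAP Section 9 ends the Treatment Period at the Month 24 visit, the ET visit or, without an ET visit, the discontinuation date. Course 1 also ends at discontinuation if that comes first. The same section gives two month lengths: 30 days for the visit schedule, and 30.4375 days for observations other than visit-related dates.

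Protocol 7.1.10 gives the Month 24 visit a window of ±7 days. On follow-up, Protocol 7.4.1.6 says "AEs are recorded and assessed continuously throughout the trial and are assessed for final outcome at the End of Trial visit"; only SAEs are to be followed beyond that visit.

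**The concern.** A prevalence needs one set of people at risk, with the cases counted inside it. Here membership depends partly on the outcome. Subjects who remain to month end are all in the denominator. Among those who exit during the month, only the fatigued are. Exit without fatigue removes a person who was observed event-free for part of the month.

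Fatigue is the only event for which the visible safety section plans a month-by-month display, and the purpose of such a display is to show a time course. The trial has a single arm, so no comparator curve would reveal an artefact. Exits are also uneven over time: nearly every completer leaves within a few days of the Month 24 visit, which falls close to a month boundary.

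**Working it through.** The documents give no fatigue prevalence and no withdrawal rate, so there is no planned figure to reproduce.

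**Inputs from the documents:** 445 subjects (Protocol Synopsis); final visit window ±7 days (Protocol 7.1.10); visit year of 360 days, counted for Course 2 from the Month 12b visit, and months of 30 or 30.4375 days (SAP Section 9).

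**Assumptions:** constant withdrawal of 5–30% over 24 months; true monthly prevalence of 5–30%; exit at mid-month; 20% of a month's cases new in that month; in step 3, final visits spread evenly over days 353–367 of Course 2 (360 ± 7); in step 4, 90% of fatigued leavers with the AE still reported as ongoing.

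**1. Direction.** Let S be the stayers, Fs the stayers with fatigue, FL the leavers with fatigue and L0 the leavers without.
- SAP: (Fs + FL)/(S + FL)
- Stayers only: Fs/S
- All present at month start: (Fs + FL)/(S + FL + L0)

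Adding FL to both terms of a fraction no greater than 1 cannot lower it, and removing L0 from a denominator cannot lower the ratio. So the SAP value is never below either consistent alternative. Example: 400 present, 40 fatigued, 20 leave, 2 of them fatigued. The SAP gives 40/(380 + 2) = 10.47%. The alternatives give 38/380 = 10.0% and 40/400 = 10.0%.

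**2. Withdrawal, counted in the exit month only.** Take 20% withdrawal and a true 10%. Month 24 starts with 359.33 subjects; 3.33 leave and 356.00 stay, so Fs = 35.60. A mid-month leaver is a case with probability 0.10 × (0.8 + 0.2/2) = 0.09, so FL = 0.30. SAP: 35.90/356.30 = 10.08%. For a true 10% at Month 24:

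| Withdrawal | Exit month only | Carried forward (step 4) |
|---|---|---|
| 5% | 10.02% | 10.38% |
| 10% | 10.04% | 10.81% |
| 20% | 10.08% | 11.79% |
| 30% | 10.12% | 13.03% |

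At the corners of the assumed ranges, a true 5% with 5% withdrawal gives 5.01%, and a true 30% with 30% withdrawal gives 30.28%.

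**3. Last month of Course 2.** If a share x of completers exits before the month ends and the true prevalence is p, the SAP reports p/(1 − x + xp).
- 30-day months: month 12 ends at day 360. Days 353–359 fall before it, so x = 7/15 = 0.467. Result: 0.10/(0.533 + 0.047) = 17.2%.
- 30.4375-day months: month 12 ends at day 365.25. Days 353–365 fall before it, so x = 13/15 = 0.867. Result: 0.10/(0.133 + 0.087) = 45.5%.

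For a true 5% the two results are 9.0% and 28.3%; for a true 20%, 31.9% and 65.2%. The size depends on x: with p = 10%, x = 0.10 gives 0.10/0.91 = 11.0%, and x = 0.25 gives 0.10/0.775 = 12.9%. At the limit x = 1, as in a displayed 13th month by whose end everyone has exited, the formula returns 100% if anyone had fatigue.

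**4. Fatigue ongoing at exit, if carried forward.** With 20% withdrawal, 445 − 359.33 = 85.67 subjects left before Month 24. Carried cases: 85.67 × 0.09 × 0.9 = 6.94. SAP at Month 24: (35.60 + 0.30 + 6.94)/(356.00 + 0.30 + 6.94) = 42.84/363.24 = 11.79%. The corners give 5.20% for a true 5% and 36.63% for a true 30%, an excess of 0.2 to 6.6 points. If leavers are fatigued at twice the stayers' rate (20% against 10%), the exit-month figure is (35.60 + 0.67)/(356.00 + 0.67) = 10.17%. Carried forward, 85.67 × 0.20 × 0.9 = 15.42 is added to both terms, giving 51.69/372.09 = 13.9%.

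**The case against.** The best defence is that the denominator is a deliberate convention. It keeps every case inside the denominator, avoids treating someone seen for part of a month as event-free, and errs on the cautious side for a safety summary. With ordinary withdrawal the cost is under 0.3 points. Stopping the drug is not leaving, because Protocol 5.5.1 and 5.5.2 keep such subjects in scheduled visits. The output is one descriptive table in an exploratory trial.

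Most of this stands, and it limits the importance of the point. It does not remove the asymmetry, because the same clause also drops completers without fatigue in the last displayed month. The size there rests on an assumed spread of visit dates; the direction does not.

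A reader might go further and infer that subjects who leave with fatigue count as cases in every later month, so that withdrawal steadily inflates the curve. The documents do not establish that. SAP 15.2.3 reports by months of the Course 1 and Course 2 Treatment Periods, and Section 9 ends those at the ET visit or discontinuation. The cap on imputed dates points the same way. What remains is ambiguity: the numerator has no in-study condition, SAP 15.1 restricts only TEAE onset, and an AE reported as ongoing gets no stop date. By contrast, the exposure-adjusted rate in SAP 15.1.1 explicitly stops at the end of the treatment period.

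A reader might also see a conflict with the Section 9 rule that "the total of missing and non-missing observations at each time-point should reflect the population still in the study at that time". That sentence concerns counts of missing and non-missing observations in tables over time. It does not define an AE prevalence, and 15.2.3 is the specific rule.

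**Conclusion.** The stated formula is biased in one direction, and that follows from algebra alone. Its size depends on assumptions.

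- Exit month, ordinary withdrawal: about 0.01 to 0.3 percentage points. This is too small to make a flat or falling prevalence look like worsening.
- Last month of Course 2: potentially large, about 17% or 45% for a true 10% depending on month length, if final visits are uniform over days 353–367.
- Carry-forward after exit: about 0.2 to 6.6 points at Month 24, but only under a literal reading that the Section 9 period ends speak against. It is a gap to close, not a demonstrated error.

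No test and no primary or secondary result uses this table. The change is still worth making, because the last point on the graph could mislead and two programmers could legitimately produce different figures.

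**What to change.** Amend SAP 15.2.3 as follows:

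1. **One at-risk set for both terms.** Denominator: subjects in the study and within that course's Treatment Period on at least one day of the month. Numerator: those of them with fatigue on at least one such day.
2. **Cap stop dates.** End every fatigue AE that is reported as ongoing or has an imputed stop date no later than the subject's own end of Treatment Period. Include subjects who never started Course 2, for whom the present limit, the end of Treatment Period 2, is undefined.
3. **State the month length.** Say which of the two Section 9 definitions applies.

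Cost: SAP wording and a small programming change, with no new data. Downside: a subject observed for only part of a month counts as fully at risk, which lowers the figure slightly. With everyone present at month start as the denominator, the calculations above give 9.99% for a true 10% at 20% withdrawal, and 29.96% for a true 30% at 30% withdrawal. Printing the number at risk under each month would let readers judge the sparse months at the end.

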15.3 Clinical Laboratory Evaluation

Lymphocyte counts from local laboratory will be used for summary statistics and shift tables. They will be classified according to the NCI-CTCAE (latest version available). The classification will be derived only from the laboratory results at a given assessment, thus ignoring the underlying syndrome.

The Treatment Course 2 can be delayed because of Lymphocyte count below 800 cells/mm³ at the Month 12 Visit. In this case, the Lymphocyte count can be measured several times between the Month 12 Visit and the start of Treatment Course 2. Lymphocyte counts at or after the visit start date of the Month 12 Visit and before or at the start date of the Treatment Course 2 will be displayed as follows:

- The earliest Lymphocyte count will be assigned to the Month 12 Visit,
- The latest Lymphocyte will be assigned to the Month 12b Visit,
- All other Lymphocyte count will be assigned to unscheduled visits.

A Lymphocyte count can be assigned to the Month 12 Visit and Month 12b Visit, if just one count is available. If the Treatment Course 2 wasn't started, only the earliest Lymphocyte count will be assigned to the Month 12 Visit.

The worst on-study grade (i.e. on or after first study treatment administration) will be summarized considering only subjects with post Baseline laboratory samples: Laboratory tests by NCI-CTCAE grade (0, 1, 2, 3, 4, any).

Lymphocyte counts will be examined for trends using descriptive statistics (mean, SD, median, Q1, Q3, minimum, and maximum) of actual values and changes from Baseline to each scheduled Visit including Month 12b Visit over time. If for a particular visit a different local laboratory than normal laboratory was used (due to COVID-19 pandemic), values collected during that visit will not be included in the descriptive statistics.

Shift tables of Baseline versus endpoint (as well as the worst value at any post-Baseline Visit) will be presented. Abnormalities classified according to NCI-CTCAE toxicity grading (latest version available) will be described using the worst grade.

All Lymphocyte counts will be listed by subject for the SAF.

Positive results of the tuberculosis and serology tests that do not comply with the protocol will be listed.

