Subjects who discontinue Mavenclad® at any time during the trial will continue to participate in the scheduled visits for assessments until his/her planned trial completion. In the event of early discontinuation from the trial, the subject should return for the Early Termination visit for final assessment.

Withdrawn subjects will not be replaced.

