7.1.8 Month 14 Visit 5 (±7 days)

Subjects will undergo**:

- A lymphocyte count as per mandatory monitoring, at local laboratory facilities *
- Review of subject diary
- Assessment of AEs, concomitant medications and concomitant procedures

*Lymphocyte count will be checked locally after 2 months of starting the 2nd course treatment. If the lymphocyte count is below 500 cells/mm³, it should be actively monitored until values increase again.

**An allowance window of 0-3 months will take place in case of delay in lymphocyte recovery to the levels mentioned in [Section 5.4.1](#).

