8.2 Definition of Analysis Sets and Subgroups

Enrolled Set (ES)

All subjects enrolled in the study, i.e. all subjects with a signed informed consent.

Intent-to-treat Set (ITT)

All subjects classified as eligible (i.e. medication assigned by iRT at the Baseline Visit).

Full Analysis Set (FAS)

All subjects from the ITT treated with at least one dose of study medication.

Treatment Completer Set – Year 1 (TCS-1)

All subjects from the FAS who completed the full Treatment Course of the first year (Treatment Course 1). Subjects will be classified as Treatment Completer for the first year, if they have a compliance greater than or equal to 100% for Treatment Course 1.

Treatment Completer Set – Year 2 (TCS-2)

All subjects from the FAS who completed the full Treatment Course of the first and the second year. Subjects will be classified as Treatment Completer for the second year, if they have a compliance greater than or equal to 100% for Treatment Course 1 and Treatment Course 2 and received the treatment without delay (see Section 9 for definition).

Safety Analysis Set (SAF)

All subjects treated with at least one dose of study medication.

Unless otherwise specified, all efficacy analyses will be performed on the FAS. The primary analysis will be repeated on the Treatment Completer Sets and on the ITT, if different, to evaluate

the sensitivity of the primary results to deviations of the planned treatment regimen. Further details are given in the respective sections. All safety analyses will be performed on the SAF.

Additional Subgroup Analysis Sets

Subgroup analyses will be performed on subgroups as defined below.

Previous treatment with Disease Modifying Drugs (DMDs):

- **DMD pre-treated:** Subjects will be categorized as DMD pre-treated if they have taken DMDs any time before start of study medication. Details of the definition of DMDs are specified in Appendix 1 (Section 18.1).
- **Pre-treatment naïve:** all subjects not classified as DMD pre-treated.

Unless otherwise indicated, all descriptive statistical analyses will be presented separately for pre-treatment naïve and DMD pre-treated subjects.

Month 12 MSQoL assessment after start of COVID-19 pandemic:

- **Yes:** Date of Month 12 MSQoL assessment (if missing, Month 12a Visit End Date) after start of COVID-19 pandemic (see Section 9 for definition).
- **No:** Otherwise.

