Treatment Period

The treatment period begins with the start of study medication on Study Day 1 and continues through to the completion of the treatment period at the Month 24 Visit (see protocol Section 7.1.3). Start of study medication is the date of first intake of study medication. Start of study medication in Year 2 is the date of first intake of study medication at or after the Month 12 Visit.

Treatment Period:

- Start = Start of study medication,
- End = Visit end date of Month 24 Visit or Early Termination (ET) Visit in case of early discontinuation, or the study discontinuation date, if the ET Visit was not performed.

Course 1 Treatment Period:

- Start = Start of study medication,
- End = Start of study medication at or after the Month 12 Visit -1 day or if the subject did not receive Treatment Course 2: Start of study medication of Treatment Course 1 + 457 days (which is obtained by 360 (12 months) + 90 (3 months) + 7 (visit window)), or date of the study discontinuation, if earlier.

Course 2 Treatment Period:

- Start = Start of study medication at or after the Month 12 Visit,
- End = End of Treatment Period.

Definition of Delayed Treatment Course 2

- The Treatment Course 2 will be defined as delayed, if the start of study medication is delayed by more than 3 months (=90 days) or did not start at all i.e.:
 - Start of Study Medication of Treatment Course 2 > Start of Study Medication of Treatment Course 1 + 457 days (which is obtained by 360 (12 months) + 90 (3 months) + 7 (visit window)), or
 - Treatment Course 2 never started (i.e. no study medication taken at or after the Month 12 Visit).

Data handling in case of a Delayed Treatment Course 2

For subjects with a Delayed Treatment Course 2, only data observed during the Course 1 Treatment Period will be analyzed in all efficacy analyses. Efficacy data after the Course 1 Treatment Period will be counted as missing in the statistical analyses and marked in the listings. In all efficacy analyses defined by Period, the subjects will be classified as if they discontinued at the end of the Course 1 Treatment Period. For subjects without a delay the whole Treatment Period will be analyzed.

For all other analyses (except efficacy) the data is not limited to the Course 1 Treatment Period for subjects with a Delayed Treatment Course 2.

Definition of start of COVID-19 pandemic

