The MSQoL-54 questionnaire has been set-up to allow only skipping of questions 46 - 49 about the Sexual function by selecting “Not applicable” as an answer. If more than one question in this part was answered, the Sexual function score will be calculated according to the scoring manual (Vickrey 1995), i.e. the mean of the answered questions will be used as score. If only one or no question was answered, the Sexual function score will be imputed with the answer of the Satisfaction with sexual function score.

CCI

CCI

14.2 Secondary Endpoint: Treatment global satisfaction assessed by TSQM v1.4 at Month 6 Visit (Interim Analysis)

The TSQM v1.4 questionnaire is a generic questionnaire to test treatment satisfaction with domains in Effectiveness, Side Effects, Convenience and Global Satisfaction and has previously been used in MS subjects (Vermersch et al., 2014). The scores will be derived according to the TSQM User Manual Version 1.0. The TSQM v1.4v scores range from 0% to 100%, with 100% being the best possible score.

At the Interim analysis, the Global Satisfaction score at Month 6 Visit will be analyzed without taking the later observations into account. At the final analysis, the Month 6 Visit will be analyzed as tertiary endpoint in a repeated model that includes the Month 12 and 24 Visit (see Section 14.3.2).

Global Satisfaction at Month 6 Visit will be analyzed at the interim analysis with a mixed linear model. The model will be adjusted for age (in years), EDSS at Baseline (≤ 3 , > 3) and within-pooled center correlations. An unstructured covariance matrix will be assumed for the model. If the model doesn't converge a variance components covariance structure will be used instead.

CCI

CCI

CCI

CCI

CCI

[figure not shown]
CCI

CCI

CCI

CCI

CCI

All volume changes will be listed by subjects.

CCI

CCI

CCI

CCI

CCI

CCI

CCI

CCI

15 Safety Analyses

The subsections in this section include specifications for summarizing safety endpoints that are common across clinical studies such as adverse events, laboratory tests and vital signs.

Safety analyses will be done on the SAF. Unless otherwise specified, the safety analysis will be done for interim and final analysis.

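### The by-visit lymphocyte table covers only Course 2 starters at Month 12b but all remaining treated subjects at Months 14 to 24, and no table gives the worst grade after Course 2

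*SAP*

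**What the plan says.** SAP 15.3 summarises lymphocyte counts by mean, SD, median, quartiles, minimum and maximum "of actual values and changes from Baseline to each scheduled Visit including Month 12b Visit over time". Counts between the Month 12 Visit and the Course 2 start are assigned to visits by rule. The earliest goes to Month 12, and "The latest Lymphocyte will be assigned to the Month 12b Visit". If Course 2 was not started, "only the earliest Lymphocyte count will be assigned to the Month 12 Visit".

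The population comes from the opening of SAP Section 15: "Safety analyses will be done on the SAF". SAP 8.2 defines that set as "All subjects treated with at least one dose of study medication", so one Course 1 tablet is enough. SAP Section 9 cuts off efficacy data for subjects whose second course is delayed or never started, but not safety data: "For all other analyses (except efficacy) the data is not limited to the Course 1 Treatment Period".

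On follow-up, Protocol 5.5.1 says that a subject who stops the drug "will continue to participate in the scheduled visits for assessments until his/her planned trial completion". Protocol 5.2 says the same for safety assessments and mandatory monitoring. Protocol 7.1.8 defines Month 14 by the second course: "Lymphocyte count will be checked locally after 2 months of starting the 2nd course treatment". Protocol 7.1.9 does the same for Month 18, at 6 months.

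For CTCAE grade, SAP 15.3 plans the worst on-study grade and shift tables from Baseline to endpoint and to the worst post-Baseline value. It plans no split by course.

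**The concern.** Severe lymphopenia is the first important identified risk named in Protocol 3.3. The effect of the second course on lymphocytes is read from the counts before it (Month 12b) and those 2 and 6 months after it (Months 14 and 18). If the group behind the columns changes at that step, the trend mixes a drug effect with a change in who is counted.

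The change is unlikely to be random. Protocol 5.4.1 requires at least 800 cells/mm³ before the second course, so the Month 12b group is selected on the variable being tabulated. Some non-starters will have been held back for persistent lymphopenia, which pulls the later means down. Others will have stopped for unrelated reasons and recovered, which pulls them up. Protocol 5.5.2 also lets non-starters receive other medication. The planned table cannot show which effect dominates.

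In addition, a severe grade first reached after Course 2 cannot be told apart from one reached after Course 1 in any planned summary table.

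**Working it through.** **Who is in each column**

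| Column | Who can contribute | Source |
|---|---|---|
| Month 12 | Any attending subject in the Safety Analysis Set | SAP 15.3 |
| Month 12b | Course 2 starters only | SAP 15.3 assignment rules |
| Months 14, 18, 24 | Starters and non-starters still attending, plus Early Termination counts mapped to the nearest missing visit | SAP 8.2, 9, 15; Protocol 5.2, 5.5.1 |

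Two further rules in SAP Section 9 bear on this. In tables over time, missing plus non-missing should equal the subjects still in the study, so non-starters belong in the later columns and at Month 12b can only appear as missing. Course 2 visits are scheduled from the Month 12b Visit, an anchor that the 15.3 rules do not give to someone who never starts.

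**Size of the composition effect**

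Let u be the undosed share of subjects with a Month 14 count, and let μD and μU be the Month 14 means in dosed and undosed subjects.

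- Displayed fall = (Month 12b mean) − [(1 − u)μD + uμU]
- Fall in starters = (Month 12b mean) − μD, ignoring dropout among starters
- Error = displayed − starters = −u(μU − μD)

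The documents give neither u nor the means, so these are assumed ranges. Scaled to the planned 445 subjects, u = 2%, 5%, 10% and 15% is about 9, 22, 44 and 67 subjects. Error in the displayed fall (cells/mm³; negative means too small):

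| u | μU − μD = −200 | +200 | +400 | +600 |
|---|---|---|---|---|
| 2% | +4 | −4 | −8 | −12 |
| 5% | +10 | −10 | −20 | −30 |
| 10% | +20 | −20 | −40 | −60 |
| 15% | +30 | −30 | −60 | −90 |

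For example, −0.15 × 600 = −90 and −0.15 × (−200) = +30. Against an assumed true fall of 500, the range is −90/500 = −18% to +30/500 = +6%.

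**Grade**

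The worst on-study grade and the shift to worst value run from the first dose to the end of the study, so a Course 1 nadir can hide or stand in for a Course 2 nadir. The shift to endpoint reports a final value, not the worst one after Course 2, and also mixes starters with non-starters.

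**What a split by treatment period would miss**

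Under SAP Section 9 a non-starter's Course 1 Treatment Period ends at the latest at start + 457 days. That figure adds up: 360 + 90 + 7 = 457. A non-starter has no Course 2 period. On the 30-day schedule Month 14 is day 420, Month 18 is day 540 and Month 24 is day 720. A non-starter's Month 18 and 24 counts would therefore fall in neither period.

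**The case against.** The strongest reply is that pooling is declared and ordinary. SAP Section 7 says that safety analyses use all data from both courses whatever the delay, and summarising all treated subjects is normal in a single-arm exploratory study. Each column correctly describes the subjects with a count at that visit. This stands as a defence of keeping the all-subject view. It does not justify a trend table whose population changes at Month 12b.

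The second reply is that much can be recovered. SAP Section 13 tabulates subjects who did not start Course 2, by whether they stopped before or after Month 12, with a row for counts below 800 cells/mm³ at Month 12. The number observed at each visit is shown, and all counts are listed by subject. This stands in part: the number of non-starters and their Month 12 status are disclosed. Their later counts are not summarised apart from those of dosed subjects.

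A reader might infer that grade 3–4 rates by visit are diluted or inflated by some number of percentage points. The documents do not support that, because SAP 15.3 plans no grade rate by visit. A reader might also take the Month 12b to Month 14 fall as a planned estimate. It is not: changes are from Baseline, and the fall is a comparison that the table invites. Nor do the later columns hold every treated subject. Only those attending or mapped from Early Termination count, and values from a different local laboratory because of COVID-19 are left out.

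**Conclusion.** The point holds as a cheap improvement. By the SAP's own rules, the by-visit lymphocyte statistics describe Course 2 starters at Month 12b and a mixture of starters and non-starters from Month 14 on. No planned summary table gives the worst grade reached after Course 2.

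Under the assumed ranges the apparent fall is between 90 cells/mm³ too small and 30 too large. With few non-starters it is only a few cells either way. Both size and direction depend on how many subjects did not start and why, which the documents cannot tell us.

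The SAP already reports by course elsewhere: SAP 15.2.3 gives the prevalence of fatigue separately for the Course 1 and Course 2 Treatment Periods. Lymphopenia, a named important risk, has no such split. The primary and secondary endpoints are unaffected.

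**What to change.** In SAP 15.3:

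1. Present Months 12, 12b, 14, 18 and 24 (values and change from Baseline) for subjects who started Course 2, with non-starters in separate rows.
2. Keep the whole-study worst CTCAE grade. Add the worst grade in the Course 1 Treatment Period and, for starters, in the Course 2 Treatment Period.
3. Show separately the non-starters' counts after their Course 1 period ends (start + 457 days at the latest), so that late or persistent lymphopenia is not lost.
4. State that the Month 12b count is pre-Course 2 even when drawn on the day Course 2 starts. SAP 15.3 allows a count on that day, while SAP Section 9 places the day in the Course 2 period.

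The cost is a few extra table rows, built from the treatment-period definitions in SAP Section 9 and the Course 2 start categories in SAP Section 13. No new data or models are needed. The non-starter rows will be small, and smaller still if also split by previous DMD treatment, which SAP 8.2 makes the default for descriptive tables. Showing them overall only would be reasonable.
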